The intervention will include a broader range of individuals [selected by glycated hemoglobin (HbA_{1c}) testing] who could benefit from lifestyle change than have been included in previous translational research studies, namely both individuals with prediabetes and those with unmedicated diabetes. This population represents the larger community of individuals at risk of developing diabetes-related outcomes and complications.

This innovative worksite-based program leverages existing worksite resources (space, health facilities, employees) to deliver the intervention package, which includes lifestyle intervention classes and broader changes in the worksite environment. Peer educators, identified from the worksite and trained by professional health educators to deliver the program, can assist in sustaining the program, offer practical suggestions for program improvement and overcoming participant barriers, and act as examples for their peers. Classes will be dynamic and group-based, including scripted lessons on health topics (to maintain fidelity to the message across sites) followed by group-based activities and discussions that can be tailored to the individual needs of each lifestyle class and worksite. The program will include four months of weekly classes on weight loss, diet improvement, increasing physical activity, and behavior change followed by an eight-month maintenance period with monthly group meetings, biweekly health related text messages, and continued support of the health education teams. The work environment will be supportive of these changes with management advising and promoting the program, allowing staff time to participate, providing staff as health educators, allowing space for classes, testing, and other study activities, covering some of the costs of testing, and making changes in canteen food offerings to adhere to the recommendations of the program.

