Preliminary data: D-CLIP [clinicaltrials.gov #NCT01283308, Emory University and Madras Diabetes Research Foundation (MDRF) investigators] is an on-going, translational, diabetes prevention study comparing standard lifestyle advice to a step-wise, culturally tailored program (group lifestyle classes plus metformin for participants not responding to lifestyle change alone) among 602 people with prediabetes in India.²⁵ D-CLIP was developed based on the DPP Curriculum.^{79,80} Early unpublished D-CLIP results are promising. The participation rate for intervention classes was high (83%), and loss to follow-up was low (9%). At eighteen months, lifestyle participants had significantly greater reductions in weight (-1.7 vs. -0.8 kg), BMI (-0.6 vs. -0.3 kg/m²), and waist circumference (-2.7 vs. -2.0 cm) than controls. Additionally, intervention participants showed greater improvements in systolic blood pressure, triglycerides, and HbA_{1c}; 21% of controls achieved improvement in two or more of these risk factors while 33% of intervention group did so. Similar to previous studies showing that weight, BMI, and waist circumference reductions significantly predicted diabetes risk reduction in lifestyle interventions,⁸¹ preliminary D-CLIP analyses show a 51% relative risk reduction in diabetes incidence in intervention participants compared to controls. The effects of the D-CLIP intervention were consistent across sex, age, income, education, and baseline BMI and glucose intolerance.⁸²

Recommendations for improving the Indian diet to better prevent diabetes and reduce cardiometabolic risk factors will be developed based on the work assessing the value of improving food quality of the Global Nutrition and Epidemiologic Transition (GNET) initiative at Harvard University and MDRF. For example, a small crossover trial of substituting brown rice for white rice for five days, found that brown rice lowered glucose levels by 19.8% and fasting insulin by 57%.⁴⁰ GNET studies in other populations further support benefits of improving carbohydrate quality.³⁸ Moreover, studies of acceptability of brown rice in India indicate that well-informed, sensory trained panelists readily accepted brown rice,³² but translating this intervention to the public

Figure 2: Components of the Lifestyle Intervention at the Individual and Worksite Environment Levels

will require additional education and training.²⁷

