Quantitative data collection (Table 4) will occur at study-testing visits at baseline and every twelve months after lifestyle classes begin. Whenever possible, validated study instruments will be used. The primary outcome assessing program effectiveness (Aim 2) will be a composite of achieving two or more cardiometabolic risk goals; participants will be scored on the number of risk factors they improve on (0-3) with success delineated by a HbA_{1c} decrease $\geq 0.5\%$; a systolic blood pressure decrease ≥ 5 mm Hg; and a decrease in plasma triglycerides ≥ 10 mg/dl. This outcome was selected for three reasons: other risk scores for CVD (e.g., the Framingham Risk Score) do not perform as well in South Asian populations;⁹³ these risk factors are commonly measured by clinicians, so the results are clinically appropriate; and the composite outcome allows for individual variation in risk factor profiles and the ability of individuals to reduce different factors (e.g., an individual with a baseline HbA_{1c} of 5.8% is unlikely to reduce this risk factor by 0.5%, but may succeed in reducing triglycerides or blood pressure).

Table 4: Quantitative Data Collection Tools

Variable of interest (test)	Outcome of test	Timing			
		S	B	A	FU
Demographics and Lifestyle Behaviors					
Demographics (SQ)	Describe study population	X	X		
History of smoking (SQ)	Smoking status and cessation rates		X	X	X
Global Physical Activity Questionnaire (GPAQ) ⁹⁴	Baseline and changes in physical activity		X	X	X
Dietary intake (food frequency questionnaire)	Study specific food frequency questionnaire on dietary intake of foods targeted in the intervention		X	X	X
Dietary behaviors (SQ)	Prevalence of diet-related behaviors (e.g., reading nutrition		X	X	X

Variable of interest (test)	Outcome of test	Timing			
		S	B	A	FU
Weight loss history (SQ)	labels, eating at restaurants, measuring portions, etc.) Weight loss history including number and success of past attempts, methods used, etc.		X		
Quality of life (EQ-5D)	Baseline and changes in quality of life		X	X	X
Self-reported health (SF-12 and SQ)	Health status, recent health events and medication use (type and dosage of all prescription and over the counter medications and herbal remedies)		X	X	X
Worker satisfaction (SQ)	Questions assessing worker satisfaction with worksite, number of days missed work, self-described levels of productivity		X	X	X
Health-related outcomes					

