Aim 2: Statistical analysis of intervention impact: A generalizing estimating equations (GEE) framework for clustered data⁹⁷ will be used to assess the statistical significance of any observed intervention effect on the endpoints. For the primary endpoint, the dependent variable will be the indicator for whether the study participant is at two or more cardiometabolic risk factor reduction goals at the end of the 3 year follow-up period, minus the expected probability of this endpoint in the absence of an intervention, to be taken as 21% as observed in the D-CLIP²⁵ control group. An exchangeable working correlation matrix will be used to incorporate the clustering within the 8 work-sites, with a log link and binomial variance specified. The exponentiated point and interval estimates from the intercept of this model will quantify the intervention effect, and the p-value associated with the model's intercept will provide a measure of the statistical significance of the findings. A similar GEE approach will be used to estimate and test the significance of intervention effects on secondary endpoints. For continuous markers, such as systolic blood pressure and HbA_{1c}, the post- to pre- within-participant difference will serve as the dependent variable in a GEE model as above, with the identity link function and the distribution specified as normal. The change scores will be evaluated for outliers, and analysis will be repeated with and without extreme outliers. For the cumulative incidence of diabetes at end of follow-up, participants will be coded as one if they satisfy the diabetes definition at end of follow-up and 0 otherwise. A Cox proportional hazards regression model for the diabetes incidence rate will also be considered, and if dropout or loss to follow-up are non-negligible, causal methods for adjusting for dependent censoring will be applied.¹⁰² A similar approach will be used to assess regression to normoglycemia. We will consider worksite-level covariates in multi-level models to examine how these aspects might affect findings. Additional secondary endpoints will be considered (e.g., changes in being at 1, 2 and 3 CVD/T2DM risk factor goals). Although the study is not powered to detect it unless quite large and although no effect modification is expected, we will assess the presence of effect modification by calculating intervention effect estimates stratified by potential modifiers, such as gender, age, marital status, socio-economic status, and assess the statistical significance of any effect modification observed by calculating a cross-product term between the potential modifier and the intervention, using a robust score test to assess the significance of

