Sample Size Selection: This worksite-clustered before-after design of 8 worksites with at least 250 eligible and enrolled participants per site and no more than 20% loss to follow-up (LTF) after 3 years will have 93% or more power to detect an estimated difference between the percent of participants at 2 or more CHD risk factor goals after 3 years of follow-up, the primary effectiveness endpoint of this trial, of 33% or greater, compared to the comparable D-CLIP²⁵ percentage of 21%. The 20% 3-year LTF rate is likely conservative, as only 9% of D-CLIP participants have been lost to follow-up after a mean of 30 months. Similarly, the D-CLIP comparative percentage of 21% is likely conservative, because the D-CLIP control group also experienced a minimal intervention that included meeting with a physician and a dietician, attending two classes (a lecture on diabetes

prevention through weight loss and diet change, and an exercise class), and receiving handouts reinforcing prevention of T2DM. Thus, compared to a community control receiving none of these services, the D-CLIP group would be expected to have a higher percentage at or exceeding two goals, compared to the community standard. In addition, power in this study is excellent for numerous secondary effectiveness endpoints of considerable interest, including 90% power or more to detect a decrease of 2mmHg or greater in systolic blood pressure ($p=0.10$, IIS), 95% power or more to detect a decrease in HbA_{1c} of 0.14% or greater ($p=0.10$, IIS), and nearly 100% power to detect a reduction in diabetes incidence of 30% or greater among the 2/3 of the study participants with prediabetes at baseline screening, compared to the baseline rate of 0.07/year,¹²⁴ otherwise under the same assumptions as the primary endpoint calculation.

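### The 21% benchmark comes from a prediabetes-only trial but is applied to a sample planned to be about one third unmedicated diabetes, so case mix may be counted as programme effect

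*Combined protocol and SAP*

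**What the plan says.** Under Data Analysis, Aim 2, the dependent variable is the indicator for reaching two or more goals at three years, "minus the expected probability of this endpoint in the absence of an intervention, to be taken as 21% as observed in the" D-CLIP control group. The model's intercept gives both the effect estimate and the p-value. No term for baseline glycaemic status is included, and every participant is measured against the same 21%.

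The source of the figure is under Approach, Preliminary data. D-CLIP was conducted "among 602 people with prediabetes in India", and "21% of controls achieved improvement in two or more of these risk factors while 33% of intervention group did so".

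The population here is wider. The Innovation section presents as a strength that the trial takes in "namely both individuals with prediabetes and those with unmedicated diabetes". The Study Sample paragraph admits HbA1c of 6.5% or more with no upper limit. Sample Size Selection gives the planned mix when it describes a secondary calculation "among the 2/3 of the study participants with prediabetes at baseline screening".

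The goals (Data Collection, quantitative data) are falls of at least 0.5% in HbA1c, 5 mm Hg in systolic pressure and 10 mg/dl in triglycerides. The same paragraph notes that a person starting at 5.8% is "unlikely to reduce this risk factor by 0.5%, but may succeed in reducing triglycerides or blood pressure".

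Sample Size Selection states that "the D-CLIP comparative percentage of 21% is likely conservative". The reason given is that D-CLIP controls received some advice and classes. Case mix is not mentioned.

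**The concern.** With no concurrent controls, the whole primary effect is the distance between the observed proportion and 21%. If 21% is not the no-programme expectation for part of the sample, that distance mixes programme effect with a difference in who was enrolled. A larger sample, GEE clustering or the planned weighting for dropout cannot remove this.

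Two features of the plan make a higher no-programme rate plausible in the diabetes stratum. First, the HbA1c goal is an absolute fall, so the room to achieve it depends on baseline HbA1c, the variable on which the two populations differ. Second, people whose screening results indicate diabetes are referred to a physician (Study Sample, screening paragraphs), so HbA1c can fall for reasons outside the programme. Medication use is recorded (Table 4), but the primary analysis does not use it.

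No planned Aim 2 analysis addresses this. Glycaemic status is not among the modifiers named there, and the marginal structural models target non-adherence and loss to follow-up. The only planned comparison of diabetes with prediabetes is for health status and utilisation (Aim 3). The external CARRS comparator depends on separate funding.

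**Working it through.** **Inputs from the documents.** Benchmark 21%; target 33%, so the planned effect is 12 points; 8 sites of 250 with 20% loss, giving 200 per site and 1,600 completers; 2/3 prediabetes, so 1/3 diabetes; alpha 0.05 (taken as two-sided).

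**Assumed.** The no-programme rate in the diabetes stratum, pD, and the intracluster correlation (ICC) for the primary endpoint. The documents give neither.

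**The plan's own power figure.** The stated 93% or more cannot be checked without an ICC, but one can be solved for. Effective n = 1,600/(1 + 199 × ICC); power = Φ[(0.33 − 0.21 − 1.96 × SE at 21%)/SE at 33%].

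- At ICC 0.047: effective n = 1,600/10.35 = 154.5; SE at 21% is 3.28 points, so the threshold is 27.42%; SE at 33% is 3.78 points; (33 − 27.42)/3.78 = 1.48, giving 93%.
- At ICC 0.10 (a 0.10 is printed beside two secondary endpoints and may be an ICC): effective n = 1,600/20.9 = 76.6 and power is about 70%.

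Both values are carried below. The case-mix bias itself does not depend on the ICC.

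**Benchmark for the planned mix.** 2/3 × 21% + 1/3 × pD = 14% + pD/3. Each 3-point excess of pD over 21% raises the benchmark by 1 point.

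**Chance of a result favouring a programme with no effect.** This is Φ[(true null − threshold)/SE at the true null]. For a true null of 25% at ICC 0.047: (25 − 27.42)/3.48 = −0.70, or 24%. At ICC 0.10 the threshold is 30.12% and (25 − 30.12)/4.95 = −1.03, or 15%.

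| Assumed pD | Mixed benchmark | Bias (points) | Share of 12 points | False win, ICC 0.047 | False win, ICC 0.10 |
|---|---|---|---|---|---|
| 21% | 21% | 0 | 0% | 2.5% | 2.5% |
| 27% | 23% | 2 | 17% | 10% | 7% |
| 33% | 25% | 4 | 33% | 24% | 15% |
| 39% | 27% | 6 | 50% | 45% | 27% |

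**What such values of pD would require.** As an illustration, assume independent goals and the same success probability q for systolic pressure and triglycerides in both strata. With HbA1c success of 5% in prediabetes, q² + 2 × 0.05 × q(1 − q) = 0.21 gives q = 0.431. Replacing 5% by b in the diabetes stratum gives pD = 0.186 + 0.490b.

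| HbA1c success b in diabetes | pD | Mixed benchmark |
|---|---|---|
| 5% | 21% | 21.0% |
| 10% | 23% | 21.8% |
| 20% | 28% | 23.5% |
| 30% | 33% | 25.1% |
| 40% | 38% | 26.7% |

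**The opposing argument on the same scale.** If the no-advice rate in prediabetes is r rather than 21%, the benchmark is (2/3)r + pD/3. It equals 21% when r = (21% − pD/3) × 3/2, which is 18% at pD 27%, 15% at 33% and 12% at 39%.

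**Power of a prediabetes-only comparison.** Completers: 2/3 × 1,600 = 1,067, or about 133 per site. At ICC 0.047 the effective n is 1,067/7.22 = 147.7 and the threshold is 27.57%; (33 − 27.57)/3.87 = 1.40, giving 92.0% against 93.0% for everyone. At ICC 0.10 it is 69.6% against 70.4%. Clustering dominates, so dropping a third of each site costs little.

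**The case against.** The strongest reply is the protocol's own: D-CLIP controls received advice and classes, so an untreated group should do worse than 21%. That is a fair argument in the opposite direction, and as shown above a modest drop would cancel a small case-mix bias. It stands as a reason not to claim a net direction. It does not validate 21% for people with diabetes, because it says nothing about them.

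A reader might infer that the diabetes stratum meets the HbA1c goal far more easily, or that case mix outweighs the minimal-advice argument so that the net error favours the programme. The documents support neither. The remark about low baselines concerns 5.8%, near the bottom of the prediabetes range, and D-CLIP's baseline HbA1c distribution is not given. The other two goals may be harder in diabetes: in the illustration, q of 35% instead of 43% with b of 20% gives 0.35² + 0.2 × 2 × 0.35 × 0.65 = 21%. Regression to the mean is also uncertain. Table 4 lists HbA1c at both screening and baseline, and if these are separate draws, selection on the screening value contributes less.

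D-CLIP effects are reported as consistent across baseline glucose intolerance. That concerns treatment effects within prediabetes, not the control rate in diabetes.

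Finally, including unmedicated diabetes is a stated purpose, so narrowing the confirmatory test changes its target population. This stands as a cost, and it is why the all-participant result should be kept.

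**Conclusion.** The population mismatch is established by the documents: a fixed 21% from a prediabetes-only trial serves as the null value for a sample planned to be about one third diabetes, with no adjustment. That it biases the comparison in the programme's favour is plausible but not shown.

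The size depends on pD, which the documents do not give: 0 points at 21%, rising to 6 points, half the planned effect, at 39%. At pD 33% the chance of a false result in the programme's favour would be about 24% (ICC 0.047) or 15% (ICC 0.10) instead of 2.5%. These are scenarios, not estimates. They rest on assumed pD and ICC, a normal approximation, the one-third planning figure rather than actual enrolment, and 21% being right for prediabetes. With the minimal-advice argument also unquantified, the net direction of error in 21% is open. A single primary test should not rest on a null value that is uncertain in this way when most of the problem can be removed using baseline HbA1c.

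**What to change.** In Data Analysis, Aim 2:

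- Make the comparison with 21% confirmatory in participants with baseline HbA1c 5.7-6.4%.
- For baseline HbA1c of 6.5% or more, report the proportion reaching two or more goals with its confidence interval and no test against 21%.
- Show the all-participant proportion against 14% + pD/3 (or the enrolled mix in place of 2:1) over a stated range of pD starting at 21%.

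In Sample Size Selection, limit the statement that 21% is likely conservative to the prediabetes group, and restate power for about 1,067 completers with the ICC used.

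No new data are needed, since baseline HbA1c is scheduled for every participant (Table 4). The cost is a smaller tested set, with power about 92% against 93% at ICC 0.047, and a confirmatory claim that applies to prediabetes only. This fix does not settle whether 21% is too high for people with prediabetes who receive no advice.

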The program evaluation will use mixed methods techniques to assess program acceptability, impact, and effectiveness. Although the goal of the program is to benefit employees, the program evaluation includes measures such as cost-effectiveness, changes in employee absenteeism/presenteeism and qualitative assessments of employee views of the program that will be beneficial to employers using or considering this program for their worksite. In addition, the acceptability and impact of the program will be measured from the perspective of multiple stakeholders – program users, employees at the worksite, and worksite management. Understanding the program outcomes and acceptability from these multiple perspectives will provide rich data for making recommendations for sustaining and disseminating the program.

Although this study will be conducted in India, the results will be applicable to workers in other settings, including the U.S. (see Foreign Justification). Asians, including Asian Indians, are the fastest growing ethnic group in the U.S., and between 2000 and 2010 the Asian Indian population increased by 67.6%.⁷¹ Furthermore, several of the companies committed to this trial (the TATA group, L&T, and Cognizant) have locations worldwide, including offices in America, and these sites would be ideal locations for first phase dissemination. In addition, lessons learned in this study would benefit U.S. companies with worksites in India.

Approach

This study will use a pre-post design at eight diverse worksites to assess program implementation, fidelity, effectiveness, and impact on study participants, workers, and the worksite. There will be no control group because there is already convincing evidence from randomized trials^{8,9,17,53,58,72} that lifestyle intervention is beneficial for preventing diabetes and diabetes-related complications. Although randomized controlled trials provide the most robust evidence for effectiveness, meta-analyses have shown that the results of non-randomized, effectiveness studies do not systematically differ from the results given by randomized controlled trials of the same treatment.^{73,74}

Intervention

The lifestyle intervention will be conducted at eight worksites (see Table 1). These worksites have large workforces (1,500-50,000 employees) and represent a range of industries with locations across India. An overview of activities to be conducted at each worksite are shown in Figure 1.

[figure not shown]

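### The 3-year primary endpoint is tested against a fixed 21% from D-CLIP controls that is undated, cannot be a full 3-year rate, and comes from people with prediabetes only

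*Combined protocol and SAP*

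**What the plan says.** Data Analysis, Aim 2, reads the primary endpoint "at the end of the 3 year follow-up period". The endpoint is reaching at least two of three risk-factor goals. From each participant's indicator the plan subtracts a constant, "minus the expected probability of this endpoint in the absence of an intervention, to be taken as 21% as observed in the D-CLIP" control group. The exponentiated intercept of a log-link GEE model is the effect estimate, and its p-value is the primary test.

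The 21% and the 33% target both come from the preliminary-data paragraph of the Intervention section, introduced by "Early unpublished D-CLIP results are promising". One sentence there is dated: "At eighteen months, lifestyle participants had significantly greater reductions in weight". The next sentence reports that "21% of controls achieved improvement in two or more of these risk factors while 33% of intervention group did so". It gives no date and does not say which cut-offs defined improvement.

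Sample Size Selection powers the trial on 33% after 3 years "compared to the comparable D-CLIP" percentage of 21%. It calls that figure conservative because D-CLIP controls received a minimal intervention. The same section states that "only 9% of D-CLIP participants have been lost to follow-up after a mean of 30 months".

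The Approach section states: "There will be no control group".

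**The concern.** The 21% defines the null hypothesis, so it has to be the success rate that these participants would show at 3 years without the programme. The endpoint counts people whose values lie a fixed amount below baseline: HbA1c by 0.5%, systolic pressure by 5 mm Hg, triglycerides by 10 mg/dl. That share need not be constant over time. Disease progression would lower it. Treatment started by participants' own doctors would raise it, and the protocol refers people with abnormal screening results to a physician.

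Population matters too. D-CLIP enrolled people with prediabetes, and Sample Size Selection assumes that 2/3 of this trial has prediabetes at baseline, so 1 − 2/3 = 1/3 has diabetes. The Data Collection section itself says that someone starting at an HbA1c of 5.8% is unlikely to fall by 0.5%. People at 6.5% or above have more room to fall, so their no-intervention rate may differ.

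With no concurrent control, such a difference is counted as programme effect or hides a real one. Because 21% is entered as a constant, the confidence interval does not reflect it.

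**Working it through.** **1. Timing, set side by side.**
- Aim 2: the endpoint is at the end of 3 years. Visits are annual, counted from the start of classes (Data Collection).
- Timeline: mean follow-up is 36 months counted from the end of the four-month core classes, so 36 + 4 = 40 months from their start.
- D-CLIP: the 21% is undated, the nearest stated time is eighteen months, and D-CLIP is described as ongoing with mean follow-up of 30 months.

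The gap is 18 versus 36 months on the natural reading. It is 30 (a mean) versus 36 on the reading kindest to the plan, and 18 versus 40 on the Timeline's clock. With a mean of 30 months, the 21% cannot be a 3-year rate for the full control group. No 3-year D-CLIP rate appears anywhere.

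**2. The plan's own power figure.** Evaluable participants: 8 × 250 × 0.80 = 1,600, or 200 per site. With effective sample size n = 1,600 / (1 + 199 × ICC), a two-sided 5% test against 0.21 has

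power = Φ[(0.33 − 0.21 − 1.96·√(0.21·0.79/n)) / √(0.33·0.67/n)].

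The ICC for the primary endpoint is not stated. A value of 0.10 is printed beside secondary endpoints only, with an unclear symbol.
- ICC 0: n = 1,600, power about 100%.
- n = 154.6: null standard error √(0.1659/154.6) = 0.0328; threshold 0.21 + 1.96 × 0.0328 = 0.274; standard error at 33% √(0.2211/154.6) = 0.0378; (0.33 − 0.274)/0.0378 ≈ 1.48; power 93%. The implied ICC is (1,600/154.6 − 1)/199 = 0.047.
- ICC 0.10: n = 76.6, power 70%.

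The stated 93% or more can be neither confirmed nor refuted. I use n ≈ 155 below as the value the plan implies.

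**3. Effect size.** On the plan's ratio scale, an observed 33% against a true no-intervention rate q gives 0.33/0.15 = 2.2, 0.33/0.21 = 1.57 and 0.33/0.27 = 1.22. These values of q are assumptions.

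**4. Chance of a significant benefit when the programme does nothing.** The test still uses 21%, but the true rate is q:

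1 − Φ[(0.21 + 1.96·√(0.21·0.79/n) − q) / √(q(1 − q)/n)].

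For n = 154.6 and q = 0.24: √(0.1824/154.6) = 0.0343; (0.274 − 0.24)/0.0343 ≈ 1.00; result 16%.

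| Assumed q | n = 155 | n = 77 (ICC 0.10) | n = 1,600 (ICC 0) |
|---|---|---|---|
| 18% | 0.1% | 0.3% | 0.0% |
| 21% | 2.5% | 2.5% | 2.5% |
| 24% | 16% | 10.5% | 83% |
| 27% | 45% | 27% | about 100% |

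The more precise the trial, the more a wrong constant matters.

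**5. The opposite direction.** Suppose q is below 21% and the programme truly multiplies success by 0.33/0.21 = 1.57. At q = 18% success is 28.3%, and the chance of a significant benefit at n = 155 is 59%. At q = 15% success is 23.6% and the chance is 13%. At q = 21% it is 93%.

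**6. Sampling error left out.** D-CLIP enrolled 602 people; arm sizes are not given. Assuming an equal split with every control measured (301), the standard error of 21% is √(0.21·0.79/301) = 0.0235. The 95% interval is 21% ± 1.96 × 2.35 points, about 16.4% to 25.6%. Fewer measured controls would widen it. The plan treats this uncertainty as zero.

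**The case against.** **The date.** The eighteen-month label belongs to the sentence on weight, BMI and waist. The 21% sentence has none, and the paragraph appears to mix data cuts: its undated 9% loss to follow-up is dated elsewhere to a mean of 30 months. A reader might infer that 21% is an eighteen-month rate. The documents do not establish that. What stands is that the rate is undated and cannot be a complete 3-year rate.

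**Drift.** No document shows the control rate changing over time, and the plausible drivers pull in opposite directions. The rates of 15% to 27% are assumptions, and n ≈ 155 is back-solved from the stated power. A reader might infer that the programme's effect will be overstated. The documents do not support any direction. This limits the claim to an uncontrolled and unreported uncertainty.

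**The plan's defence.** Sample Size Selection calls 21% conservative because D-CLIP controls received some advice. That is a fair point about treatment content, but it does not address time or population.

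**Other safeguards.** The section on future plans proposes an external longitudinal cohort (CARRS) to adjust for secular trends. It is a post-closeout analysis dependent on separate funding, so it does not repair the primary test. The marginal structural models in Aim 2 address non-adherence and loss to follow-up, not the reference rate.

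**Population.** That a 0.5% HbA1c fall is easier to reach in diabetes extends what the protocol says. It remains true that D-CLIP does not represent about one third of the participants.

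**Conclusion.** The concern holds in this form: a 3-year result is tested against a constant that is undated, cannot be a complete 3-year rate, comes from a prediabetes-only trial and carries no sampling error. Nothing in the primary analysis corrects for this.

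The size is conditional. At n ≈ 155, with assumed true no-intervention rates of 24% and 27%, the false-benefit rate is about 16% and 45%, against 2.5% if 21% is right. At ICC 0.10 the two figures are about 10% and 27%. A true rate below 21% would work against the programme instead.

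A reader might also conclude that the 93% power is wrong. That does not follow, because the ICC behind it is not stated and the point does not depend on it. The 33% target does share the same undated source.

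This should be fixed. With no documented drift and no known direction, it does not show that the trial's conclusion would be wrong.

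**What to change.** Before outcomes are analysed:
- State when the 21% was measured and with which cut-offs.
- Replace it, in Aim 2 and in Sample Size Selection, with the D-CLIP control rate recomputed with this trial's three cut-offs at the D-CLIP visit closest to this trial's endpoint time. Time both trials from baseline, and first reconcile the 3-year endpoint with the Timeline's 36 months from the end of core classes.
- Carry the sampling error of that rate into the confidence interval and the test, and pre-specify a sensitivity range for it.
- Report the D-CLIP comparison in participants with prediabetes at baseline, beside the all-participant result.
- If D-CLIP has no visit near 3 years, add a comparison at this trial's annual visit closest in time to the latest D-CLIP control visit (the earlier one if tied, as 24 and 36 months would be for a 30-month visit), and describe the 3-year comparison as not time-matched.

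The cost is one re-tabulation by institutions that run D-CLIP and are partners here, plus revised wording. It does change the null value of the primary test and the basis of the sample size, and both may become less favourable. At n ≈ 155, power for a true 33% would be 73% against a reference of 24% and 40% against 27%, and somewhat lower once the reference rate's own error is included.
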